All the relevant data will be compiled on a master chart first and then statistical analysis of the results will be obtained by using Windows based computer software facilities with Statistical Packages for Social Sciences (SPSS-24) (SPSS Inc, Chicago IL USA). The data will be analysed using Chi-square test and 't' test. The results will be presented in tables, figures, diagrams. All reported P values are two sided and $P < 0.05$ will be considered statistically significant.

Title of the Protocol

Free Breathing versus Deep Inspiration Breath Hold Technique in Adjuvant Radiotherapy for Left Sided Breast Cancer: A Dosimetric Comparison of Target Volumes, Heart and Left Lung

Name of the student : [name]

Place of study : Department of Clinical Oncology, BSMMU

: Department of Radiation Oncology, Combined Military Hospital

: Department of Oncology, Delta Hospital Limited

: Lab Aid Cancer Hospital

Type of the study : Quasi-Experimental study

Name of the guide : [name]. [name]
Associate Professor
Department of Clinical Oncology
Bangabandhu Sheikh Mujib Medical University (BSMMU)

Table of Contents

Serial No.	Topic	Page No.
1	Title	-
2	Introduction	1
3	Rationale of the study	6
4	Research question	7
5	Objectives	8
6	Materials & Methods	9
	a) Study design	9
	b) Duration of study	9
	c) Centre of study	9
	d) Study Population	9
	e) Sampling technique	9
	f) Sample size	10
	g) Selection criteria of patients	11
	h) Research Instrument	11
	i) Grouping	12
	j) Study procedure	12
	k) Case collection	14
	l) Pre-treatment evaluation	14
	m) Intervention	15
	n) Variables	15
	o) Data collection	16
	p) Consort flow chart	17
	q) Operational definition	18
	r) Analysis of Data	20
	s) Data presentation	20
	t) Quality assurance	20
	u) Timetable of the study	21
7	Ethical Considerations	22
8	Dummy tables	23
9	Limitations of the study	24
10	Reference	25
11	Budget	32
12	Appendices	Xiv

Introduction

“Cancer is a large group of diseases that can start in almost any organ or tissue of the body when abnormal cells grow uncontrollably, go beyond their usual boundaries to invade adjoining parts of the body and/or spread to other organs” (World Health Organization [WHO]). The incidence, prevalence and fatality of cancer is rising worldwide with the increase in life expectancy and change in lifestyle. It represents a significant global health, social and economic burden.

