Maximum western studies recommend to adopt this technique for eligible left sided breast cancer patients by proving the efficacy of DIBH RT to reduce heart and left lung doses with better dose delivery to the PTVs. In countries with limited resources, it is important to distribute the available resources accordingly for best treatment outcome. DIBH RT seems to be more effective, practicable and economically feasible compared to other modalities for cardio pulmonary sparing. Thereby, it may help to decrease future disease load and the associated economic burden both for the patients and the nation.

To the best of my knowledge, there is no study comparing target volumes, heart and left lung doses in FB RT and DIBH RT in our population. So, this study will be carried out to compare the dosimetric benefits of the DIBH technique during left sided PMRT over FB RT. This study may help to optimize PMRT approaches.

Research Question

Does deep inspiration breath hold technique in adjuvant radiotherapy for left sided breast cancer reduces doses to the heart and left lung without compromising target volume doses?

Objectives

General Objective:

To compare radiation doses of target volumes, heart and left lung by free breathing technique and deep inspiration breath hold technique in adjuvant radiotherapy for left sided breast cancer.

Specific Objectives:

1. To evaluate target volume doses during adjuvant radiotherapy for left sided breast cancer with free breathing and deep inspiration breath hold technique.
2. To assess cardiac doses during adjuvant radiotherapy for left sided breast cancer with free breathing and deep inspiration breath hold technique.
3. To analyse left lung doses during adjuvant radiotherapy for left sided breast cancer with free breathing and deep inspiration breath hold technique.
4. To demonstrate other organ at risks (right lung, right breast, esophagus, spinal cord) doses during adjuvant radiotherapy for left sided breast cancer with free breathing and deep inspiration breath hold technique.
5. To observe different demographic variables.

Materials & Methods

Study Design

Quasi-Experimental study

Duration of Study

One year after approval from Institutional Review Board (IRB) of BSMMU.

Centres of Study

This study will be conducted in-

1. Department of Clinical Oncology
Bangabandhu Sheikh Mujib Medical University (BSMMU)
[name].
2. Department of Radiation Oncology
Combined Military Hospital

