[name].
3. Department of Oncology
Delta Hospital Limited
[name].
4. Lab Aid Cancer Hospital
[name].

Study Population

Carcinoma left breast patients attending the outpatient departments (OPD) of study centres for post mastectomy radiotherapy.

Sampling Technique

After meeting inclusion and exclusion criteria, participants will be enrolled in this study and then divided equally into 2 arms by purposive sampling.

Sample Size

For determination of sample size following formula has been applied:

$$n = \frac{2 \times \sigma^2 \times (Z_\alpha + Z_\beta)^2}{(\mu_1 - \mu_2)^2}$$

n = Sample size

μ_1 = Mean of control group (From previous study)

μ_2 = Mean of experimental group (From previous study)

σ = Standard deviation (SD) of control group

Z_α = Z- value (two tail) at a given level of significance e.g. 1.96 at 5% level of significance

Z_β = Z- value (two tail) at a given power e.g. 1.28 at 90% power

PMRT in free breathing technique is expected to give radiation doses to $V_{25\%}$ of heart in 2.5 (SD 2.4) Gy (Rochet, et al., 2014).

PMRT in DIBH technique is expected to give radiation doses to $V_{25\%}$ of heart in 0.1 (SD 0.2) Gy (Rochet, et al., 2014).

Here,

$$\mu_1 = 2.5$$

$$Z_\alpha = 1.96$$

$$\mu_2 = 0.1$$

$$Z_\beta = 1.28$$

$$\sigma = 2.4$$

$$n = \frac{2 \times 2.4^2 \times (1.96 + 1.28)^2}{(2.5 - 0.1)^2} = 23$$

With a 10% allowance for lost to follow up final sample size is $23 + 2.3 = 25$

Selection of Patients

Participants will be selected after fulfilment of inclusion and exclusion criteria.

Inclusion Criteria

1. Histopathologically proven left sided invasive breast cancer patients who underwent modified radical mastectomy.
2. Post mastectomy patients for whom radiotherapy including supraclavicular irradiation is indicated.
3. Patients having ECOG performance status up to 1.

Exclusion Criteria

1. Left sided breast cancer patient underwent BCS.
2. Patient received any chemotherapy other than Doxorubicin, Cyclophosphamide and taxane (Paclitaxel/ Docetaxel) in any settings (neoadjuvant or adjuvant).
3. Patients who have comorbidities that would hinder DIBH (extreme obesity, mental disorder, hypoacusis etc.).
4. Known case of patients with respiratory diseases.
5. Known case of patients with ischemic heart diseases.
6. Patients with previous history of radiotherapy to chest.
7. Male breast cancer patients.

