In BSMMU, data acquired by CT scanner and sentinel will be transferred to central database for automatic tracking of same surface points and breathing pattern with a Catalyst™ system in the treatment room during every fraction, without any manual intervention. IMRT planning will be done by Monaco® Treatment Planning Software (TPS) 5.11 (Elekta AB, Stockholm, Sweden) consist of 6 MV tangential beams.

In other institutes, data will be imported to console automatically from RGSC and RPM™ and a treatment gate window will be established. IMRT planning will be done using TPS Eclipse v15.1 (Varian Medical Systems, Palo Alto, CA, USA) in CMH and v16.1 in Lab aid.

Plans will be evaluated using dose constraint as MSKCC dosimetric planning guidelines for breast IMRT: for heart- $V_{25Gy} < 25\%$, mean dose, $D_{mean} < 20Gy$, maximum dose, $D_{max} \leq 53$ Gy; for lungs- $V_{20Gy} \leq 30\%$, mean dose, $D_{mean} \leq 22$ Gy.

Case Collection

From the OPD of study centres, a total of 50 participants will be recruited after justifying inclusion and exclusion criteria. Before participating in the study, written informed consent will be taken from each selected participant. Interviews will be taken focusing their medical and relevant history by the researcher and will be documented in the preformed data-sheet in respected department with proper privacy. Also, necessary clinical examinations and investigations will be done. Many left sided post mastectomy patients come to these centres regularly for PMRT from all over Bangladesh. Therefore, it will be easy to enrol an adequate number of participants.

Pre-treatment Evaluation

Following procedures will be done to evaluate the participant's condition before treatment:

General examination:

- Complete history, performance status and general physical examination including supraclavicular lymph nodes.

Local examination:

- Right breast examination including draining lymph node areas.
- For left side, chest wall, scar and axilla.

Systemic examination:

- Respiratory system examination.
- Cardiovascular system examination.

Investigations:

- Plain chest radiograph PA view
- ECG
- Echocardiography
- Lung function test

Along with these, all pre surgical imaging and reports will be thoroughly checked.

Intervention

All participants will receive RT with Elekta Versa HD (Elekta AB, Stockholm, Sweden) machine in BSMMU and Varian TrueBeam (Varian Medical Systems, Palo Alto, CA, USA) in other institutes.

Arm A: FB RT arm

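### The research question asks whether breath hold leaves target dose uncompromised, but the only stated inference is a difference test, with no margin or listed PTV criterion by which that could be shown

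*Protocol*

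**What the plan says.** - **Research Question:** asks whether DIBH "reduces doses to the heart and left lung without compromising target volume doses". The abstract's background makes the same point about the PTV.
- **Objectives, specific objective 1:** "To evaluate target volume doses during adjuvant radiotherapy for left sided breast cancer with free breathing and deep inspiration breath hold technique". It gives no criterion for deciding that target dose has been preserved.
- **Abstract, Statistical Method:** "The data will be analysed using Chi-square test and 't' test", and "All reported P values are two sided and $P < 0.05$ will be considered statistically significant". Analysis of Data adds the software and says that the analysis follows the objectives.
- **Sample Size:** built on heart V25 only ("PMRT in free breathing technique is expected to give radiation doses to" V25% of heart, 2.5 with SD 2.4, against 0.1 with SD 0.2 for DIBH), with Z-beta "at a given power e.g. 1.28 at 90% power". The result is 23, raised to 25 per arm.
- **Treatment Planning and Evaluation:** "Plans will be evaluated using dose constraint as MSKCC dosimetric planning guidelines for breast IMRT: for heart", followed by heart and lung values. No PTV value is listed.
- **Variables:** PTV total volume, maximum dose, mean dose and V95, with no expected value, SD or acceptance level.

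**The concern.** The research question has two halves that need different evidence. Showing that heart and lung dose fall is a question of difference, and a two-sided t test suits it. Showing that target dose is not compromised is a question of non-inferiority. A difference test cannot answer it: a P value of 0.05 or more is what one sees when coverage is preserved, and also when coverage has fallen but the sample is too small to show it. This would hold with a single target variable and a single test, so it is separate from the choice of primary outcome and from multiplicity.

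At stake is how the organ sparing is interpreted. Sparing can be bought with target coverage, and the Introduction itself notes that shielding the heart may underdose the PTV. If coverage differed between the arms, part of any reduction in heart or lung dose might not be a gain from breath hold. The conclusion the protocol hopes for, sparing at no cost to the target, could then rest on low power.

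**Working it through.** **1. The plan's own figure.** Sample Size inputs: means 2.5 and 0.1, SD 2.4, z values 1.96 and 1.28.

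n = 2 × 2.4² × (1.96 + 1.28)² / (2.5 − 0.1)² = 2 × 5.76 × 10.4976 / 5.76 = 20.995, so 21 per arm (22 with unrounded z values).

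The protocol prints 23, a small difference on the safe side and not part of this point. The 10% allowance gives 23 + 2.3 = 25.3, taken as 25. No PTV quantity enters the calculation.

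**2. What the stated test can see on a PTV measure.** Assumptions: normal data, equal SDs, independent arms. As the protocol gives no PTV SD, losses are in SD units.

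Largest non-significant observed difference with 25 per arm: t(0.975; 48 df) × √(2/25) = 2.011 × 0.2828 = 0.569 SD. This is also the half-width of the 95% confidence interval.

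Probability of missing a true loss d: the noncentral t distribution with 2n − 2 df and noncentrality d × √(n/2), evaluated at the critical value.

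| True loss (SD) | Missed, 25 per arm | Missed, 23 per arm |
|---|---|---|
| 0.2 | 90% | 90% |
| 0.3 | 82% | 83% |
| 0.5 | 59% | 62% |
| 0.6 | 45% | 49% |
| 0.8 | 21% | 24% |
| 1.0 | 7% | 9% |

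The chance of missing the loss passes 50% below about 0.57 SD with 25 per arm, or 0.59 SD with 23.

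**3. The same in percentage points, with assumed SDs.** For a 2-point loss in V95 and 25 per arm, power is 93% if the SD is 2 points, 64% if it is 3 and 28% if it is 5. The documents do not say which applies.

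**4. What 25 per arm could support as non-inferiority.** One-sided 2.5% (the lower limit of a 95% interval), true difference zero, margin m in SD units: n = 2 × (1.96 + z for power)² / m².

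| Margin (SD) | n per arm, 80% power | n per arm, 90% power |
|---|---|---|
| 0.3 | 175 | 234 |
| 0.5 | 63 | 85 |
| 0.8 | 25 | 33 |
| 1.0 | 16 | 22 |

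Solving for m at n = 25: (1.960 + 0.842) × 0.2828 = 0.79 SD at 80% power, and (1.960 + 1.282) × 0.2828 = 0.92 SD at 90%.

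**5. The measure itself.** In Operational Definition, V5, V20 and V25 are each the share of a structure's volume receiving at least a stated dose. The V95% entry instead fixes the volume at 95% and still expresses the result as a percentage of volume. A margin cannot be attached until it is clear what is measured.

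**The case against.** The strongest reply is that the protocol declares no non-inferiority aim. Its objectives are neutral (to compare, to evaluate), and the preservation wording is a research question, not a success criterion. How a PTV result is worded, and whether intervals are reported, could be left to a statistical analysis plan, which was not available here. This has some force, but the protocol is not silent on inference. It names the tests, the sidedness and the threshold, and they do not fit half of its own question. A margin also decides whether 50 patients can answer that half, so it belongs before enrolment.

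Four stronger readings are tempting, and the documents do not support them:

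- **The protocol will report a P value of 0.05 or more as no compromise.** No section says so. It is a risk, because no other rule is given.
- **A real loss would usually be missed.** This is true only below about 0.57 SD. At 0.8 SD the test detects the loss 79% of the time, and at 1.0 SD 93%. Without a PTV SD or a relevant loss, the documents cannot show which case applies.
- **Nothing keeps coverage equal between arms.** Both arms share the prescription, the fractionation, IMRT and the contouring rules, and the cited planning guideline may contain target limits that are not reproduced. What can be said is that no PTV limit is listed.
- **DIBH is expected to lose coverage.** The Introduction and Rationale suggest equal or better target dose. The point is that the stated analysis could not confirm this.

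**Conclusion.** The point holds. The research question calls for a not-worse conclusion on target dose, while the stated inference is a test for a difference, with no margin, no interval rule and no listed PTV criterion. Followed exactly, the plan cannot establish the target half of its question at any sample size. With 25 per arm, a non-significant result is compatible with sizeable losses: one of 0.5 SD would be missed 59% of the time. The percentages assume normal data and equal SDs. V95 is bounded at 100% and may be skewed, so they are a guide. The logical defect does not depend on them. It should be corrected before enrolment.

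**What to change.** 1. In Operational Definition, rewrite V95% in the form of the other Vx entries, as the share of the PTV's volume receiving at least a stated dose level, with the sponsor naming that level.
2. In Objective 1 and Analysis of Data, state that the target part is judged by the 95% confidence interval for DIBH minus free breathing in PTV V95, against a largest acceptable loss in percentage points that the sponsor writes down before enrolment.
3. Claim that target dose is not compromised only if the lower limit lies above minus that margin. Otherwise give the interval and say only that no difference was detected or, if the whole interval lies below zero, that coverage was lower. Do not use a non-significant P value as support.
4. State the limits. With 25 per arm, only a margin of about 0.8 SD is supported at 80% power. Because Sampling Technique and Grouping form the arms by purposive sampling, an interval that clears the margin does not remove selection bias.

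The cost is protocol wording and one interval, with no new data. Keeping 50 patients means that the claim may not be reached. If the sponsor wants a tighter margin to be attainable, more patients are needed: 63 per arm for 0.5 SD at 80% power, 85 at 90%.

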8. Bilateral breast cancer patients.
9. Pregnant or lactating women.
10. Age < 18 years.

Criteria of Discontinuation of Treatment

1. Patient's refusal to continue study participation.
2. Justifiable withdrawal at the investigator's discretion.
3. Occurrence of unacceptable issues requiring major modification of treatment.
4. Clear lack of clinical benefit.

Research Instrument

A semi-structured data collection form consisting of sociodemographic information, relevant history, clinical examination and investigations made by the researcher will be used as research instrument (**appendix IV**).

Grouping

Fifty post mastectomy left sided breast cancer patients who meet the inclusion and exclusion criteria will be enrolled in this study. Then they will be divided equally into 2 arms (Arm A and Arm B) by purposive sampling.

Study Procedure

For Arm A participants, CT simulation scans will be performed on a supine breast board by Brilliance, CT Big Bore (Philips, Cleveland, USA) in BSMMU, Biograph mCT Sim edition (Siemens Healthineers AG, Germany) in CMH and Somatom 16 CT (Siemens Healthineers AG, Germany) in other institutes with arms raised above head in supports with free breathing. The board will be angled around 5°-25°, to level participant's chest as horizontal as possible. The head will be extended comfortably with face turned to the right side. Radio-opaque wires will be placed over surgical scars. Skin markers, room laser alignment, and breast-board scale will be used for standard patient positioning. Scans will be acquired with a 4 mm slice width from above the shoulder to include the neck to 5.0 cm below inframammary fold (using right inframammary fold as reference).

For Arm B participants, procedure will be same except the following-

Breath Holding Technique

Participants will be trained for 2-3 days for obtaining the desired breathing cycle by trained technologists. No extra equipment will be needed. At first, they will be assured and asked to relax. Then instructed to breath in and out twice followed by a slow, deep breath in to a comfortable higher level than normal and to hold it for at least 20 seconds then again breath normally. Once they are ready with expected breath holding, simulation will be done.

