During this procedure in BSMMU, SGRT system (C-RAD, Uppsala, Sweden) will be used. At the time of simulation with this system, no marker is usually needed on or around the participant; ceiling mounted laser tracking system in the room automatically monitor for consistency by matching with anterior and lateral tattoos.

In CMH, Varian RGSC (Respiratory Gating for Scanners) and in other institutes, Varian RPM™ system (Varian Medical System, Palo Alto, CA) will be used. A 4-dotted reflective marker box will be placed outside the treatment field between xiphoid level and umbilicus. It will act as an external surrogate to simulate the breathing pattern and tracked by the infrared camera at the foot end of CT couch.

For all patients, audio-visual communication through in-room speakers will assist the participant to follow the optimal breathing pattern. Each participant will have 2 CT simulation scans in this arm. One just like participants in Arm A with FB, used as the reference for treatment setups; and another in DIBH position used for the actual treatment plan.

A 30-35 minute in-room time (which included participant's dressing and undressing, set-up, daily imaging, DIBH practice, and subsequent gated RT delivery) was given to each participant for first RT day. For subsequent days, 15–20-minute time was enough, which is double than the allocated time for radiation delivery with FB.

Contouring

For all participants, contouring will be done as per the Radiation Therapy Oncology Group (RTOG) protocol. For left chest wall, superiorly caudal border of the clavicle head, inferiorly loss of CT apparent right breast tissue, laterally mid axillary line excluding latissimus dorsi muscle, medially sternal–rib junction, posteriorly rib–pleural interface, anteriorly skin will be drawn. Nodal area will be contoured including supraclavicular field. For heart, the superior point is where pulmonary trunk and right pulmonary artery seen separately. The major blood vessels will be excluded but the left anterior descending (LAD) artery will be included in the heart contour as a whole. Lungs and other OARs will be contoured accordingly using the planning system.

Treatment Planning and Evaluation

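### Patients are placed in the free-breathing or DIBH arm purposively, with no stated random element or within-centre balance, so the between-arm tests can mix patient selection, and to a lesser degree centre mix, with the effect of technique

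*Protocol*

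**What the plan says.** Allocation is described twice in the Protocol. Under Sampling Technique, "participants will be enrolled in this study and then divided equally into 2 arms by purposive sampling". Under Grouping, for the fifty eligible patients, "Then they will be divided equally into 2 arms (Arm A and Arm B) by purposive sampling". Equality refers to the overall arm sizes. No visible text gives a random element, an allocation rule or a balance by centre.

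The Research Question is causal: whether DIBH "reduces doses to the heart and left lung without compromising target volume doses". The abstract's Statistical Method names the chi-square and t tests. Limitations of the Study concedes that machine and treatment protocol vary by centre and that existing risk factors are not adjusted for. The study is labelled quasi-experimental.

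Some features narrow the problem. Exclusion criteria 3 to 5 apply to both arms: the third removes "Patients who have comorbidities that would hinder DIBH (extreme obesity, mental disorder, hypoacusis etc", and the next two remove known respiratory and ischaemic heart disease. Type of surgery and fractionation are fixed. Contouring rules and planning constraints are shared: "For all participants, contouring will be done as per the Radiation Therapy Oncology Group (RTOG) protocol", and "Plans will be evaluated using dose constraint as MSKCC dosimetric planning guidelines for breast IMRT".

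Each Arm B patient has two planning scans. One is in DIBH; the other is described as "One just like participants in Arm A with FB, used as the reference for treatment setups".

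**The concern.** If a person chooses the arm, the choice can follow features that also determine heart and lung dose. The Introduction supplies such features. It says that BMI, structural abnormality, adherence of the heart to the chest wall and patient cooperation often limit the feasibility of DIBH. It also says that DIBH is of more benefit where cardiac dose is likely to be high. The first consideration would send favourable anatomy to DIBH and the second unfavourable anatomy, so neither the sign nor the size of a resulting bias can be known in advance.

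Centre is a second route. Study Procedure, Treatment Planning and Evaluation, and Intervention describe three scanner and gating set-ups, two linac types, and Monaco 5.11, Eclipse v15.1 or Eclipse v16.1 where planning software is named. By the Operational Definition, mean and maximum doses come from the planning system's own algorithm. If the arms draw unequally on the centres, those differences enter the comparison.

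At stake is whether a difference, or its absence, can be attributed to the technique for heart, left lung and PTV.

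**Working it through.** **Inputs.** From Sample Size: heart V25 mean 2.5 (SD 2.4) in free breathing and 0.1 (SD 0.2) in DIBH, z values 1.96 and 1.28, 25 per arm after a 10% allowance. From the abstract: two-sided 5% tests. Every imbalance below is an assumption, because the documents give none.

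**1. The plan's own figure.** n = 2 × 2.4² × (1.96 + 1.28)² / 2.4² = 2 × 10.4976 = 20.995, so 21 by the printed formula against the stated 23. A t-based calculation for 90% power gives 23. Then 23 + 2.3 = 25.3, stated as 25. Power at 25 per arm for a 1 SD difference is 93.4%. None of this depends on how patients are allocated, so the sample size gives no protection against bias.

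**2. Imbalance with no true effect.** For a shift of b SD, the t statistic has 48 df and noncentrality b × √(25/2) = 3.536b.

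| Shift (SD) | Rejects in direction of shift | Rejects in opposite direction | Total |
|---|---|---|---|
| 0.10 | 5.3% | 1.1% | 6.4% |
| 0.25 | 13.7% | 0.2% | 13.9% |
| 0.50 | 41.0% | 0.0% | 41.0% |

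The shift may favour or disfavour DIBH.

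**3. Imbalance against a real effect.** With 25 per arm, an effect of 0.81 SD has 80% power. Reduced by 0.1, 0.25 or 0.5 SD, it is detected with 69%, 49% or 19% power.

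**4. Centre mix.** Suppose one centre supplies 15 Arm A and 10 Arm B patients, and its doses lie 0.5 or 1 SD higher. The shift between arms is (15 − 10)/25 × offset = 0.2 × offset, that is 0.1 or 0.2 SD. Putting these shifts into the step 2 calculation would give 6.4% or 10.7%, but that is too high. The mixture also widens the spread inside each arm (for a 1 SD offset by 0.6 × 0.4 × 1² = 0.24 in variance), and the t test counts this in its standard error. Simulating the scenario with normal data gives about 5.6% and 7.0 to 7.4%, depending on whether the SD is defined within centre or in total.

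**5. Heart V25.** The planned difference is 2.5 − 0.1 = 2.4, which is 1 SD. An imbalance of 0.5 SD (1.2) would move the expected difference to 1.2 or 3.6. About 1 SD of imbalance is needed to erase it.

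**6. What a paired comparison in Arm B could deliver.** The SD of the paired difference is √(2.4² + 0.2² − 2r × 2.4 × 0.2), which is 2.60 at r = −1 and 2.20 at r = 1. With 25 pairs, power for heart V25 exceeds 99% at any correlation. The 95% CI half-width is 0.91 to 1.07, against 0.99 for the two-arm comparison. For lung and PTV, assuming equal SDs, the difference detectable with 80% power is 0.584 × √(2(1 − r)): 0.83, 0.58 or 0.37 SD at r = 0, 0.5 or 0.8, against 0.81 SD for two arms of 25.

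**The case against.** The study calls itself quasi-experimental, and its limitations list admits the centre differences and the lack of adjustment. Eligibility, surgery, schedule, contouring and planning constraints are restricted or common to both arms. The one endpoint with planning figures has a margin of a full SD. All of this is fair. It makes the point an acknowledged design weakness and not a contradiction. It does not remove the bias, however, and the purposive division is not itself among the listed limitations.

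Several stronger readings are tempting and are not supported:

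- *Centre mix alone would seriously inflate false positives.* Step 4 gives only about 7% for a 15/10 split and a 1 SD offset. Nor is centre aliased with arm: both arms are described across the centres, and only the split within centre is left open.
- *Lung and PTV results have no margin.* The protocol gives no effect size for them, so the margin is unknown, not absent.
- *Arm B loses patients who fail breath-hold training.* The text says "Once they are ready with expected breath holding, simulation will be done". It does not say that anyone is dropped or moved.
- *Centre will go unadjusted.* The limitation speaks of existing risk factors. Adjustment for centre could properly be set out in a statistical analysis plan that is not shown.
- *The paired comparison should replace the two-arm one.* That would demote Arm A and leave the purposive wording untouched. The paired result would also describe only patients placed in Arm B.

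**Conclusion.** The concern holds as a weakness in how the protocol fixes allocation. Followed as written, the plan lets the choice of arm depend on features related to dose, and the between-arm tests cannot separate this from the technique.

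The size cannot be derived from the documents. The 6.4%, 14% and 41% figures rest on assumed imbalances of 0.1, 0.25 and 0.5 SD, and nothing in the protocol shows which, if any, will occur. Patient selection is the main route; centre mix is the smaller one. A reader might infer that the heart finding would be spurious. That is not supported: the planned heart V25 difference would probably survive, though its estimated size could be distorted. For left lung and PTV, the other two parts of the research question, a false difference or a missed real one is possible, and how likely either is cannot be stated.

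**What to change.** **Allocation.** In Sampling Technique and Grouping, replace the purposive division with 1:1 random allocation in blocks within each centre, made after eligibility and consent are confirmed. Change the design label, consent text and ethics submission to match.

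**Paired comparison, in addition, or instead if allocation stays non-random.** In Treatment Planning and Evaluation, state that each Arm B patient's free-breathing scan will also be contoured and planned, under the same contouring rules and planning constraints as the DIBH scan and for dosimetric comparison only. In Analysis of Data, state that the paired DIBH-minus-free-breathing difference with its 95% CI will be reported for each heart, left lung and PTV endpoint beside the between-arm comparison, and that it applies to patients placed in Arm B who completed breath-hold training.

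**If allocation stays non-random,** also balance the arms within each centre and record centre for every patient.

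**Cost.** Contouring and planning time for up to 25 scans that will exist anyway. Randomisation adds one list per centre and amended consent and ethics documents. Neither change needs an extra scan, visit or patient. Allocation has to be settled before enrolment, because it cannot be repaired afterwards.
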